Date: February, 2022

STUDY PROTOCOL

**Administration of ONS Based on Purple Sweet Potato in Head and Neck Cancer Patients With
Radiotherapy**

[name]

**Universitas Brawijaya
Malang, East Java, Indonesia**

INTRODUCTION

A. Background

Cancer was the first and second most common cause of death before the age of 70 in 91 of 172 countries in the world in 2015 (Bray et al., 2018). One type of head and neck cancer (HNC), namely nasopharyngeal cancer, is ranked the 4th most common cancer in men and the 5th most common in both men and women (World Health Organization, 2019).

Cancer patients are at risk of experiencing malnutrition caused by changes in metabolism and pathophysiology of cancer itself, as well as side effects of cancer treatment or therapy. Malnutrition occurs in most (74%) of HNC patients with radiotherapy. Radiation to the head and neck area causes damage to the mucosa cells and salivary glands. It changes in taste, xerostomia, mucositis, pain, and hypophagia resulting in malnutrition. Its symptoms are decreased food intake, reduced body weight by 5%, decreased upper arm circumference, and reduced serum protein and albumin levels (Citak et al., 2019; Nicolini et al., 2013).

One of the nutritional interventions that can be given to prevent and treat malnutrition is administering oral nutritional supplements (ONS). ONS is part of nutritional support or medical nutrition therapy (MNT) in the form of oral food intake supplementation given for particular medical purposes in addition to a regular diet. The ONS form is usually ready-to-drink liquid or ready-to-boil powder but can also be used as a dessert or snack bar (Cederholm et al., 2017; Lochs et al., 2006). High protein ONS enriched with omega-3 in cancer patients can increase body weight, maintain muscle mass, reduce inflammatory response by lowering C-reactive protein (CRP) levels, and improve several domains of quality of life. Such as global health scores and cognitive and physical functioning (Schueren et al., 2018).

Formulating ONS can be made using local food ingredients that have been processed and prepared in powder form, ready to be brewed so that it is easy and practical for patients without mixing food ingredients in fresh conditions (Susetyowati et al., 2019). One of the local food ingredients widely developed in Malang, East Java, is purple sweet potato. Purple sweet potato is rich in anthocyanins, where the highest anthocyanin content is found in the Antin 3 variety, containing 133.39 mg/100 g (Daniela Ticoalu et al., 2016). Anthocyanin colour pigments could modulate the activity of various targets in carcinogenesis through direct interaction or modulation of gene expression and inhibit the growth of cancer cells. The potential antioxidant capabilities of anthocyanins have been seen in vitro studies using cancer cell cultures of the ovary, colon, liver endothelial, breast, and leukemia cells. Anthocyanins have anti-proliferative and anti-carcinogenic effects (Chen et al., 2015; Diaconeasa et al., 2017).

Another food ingredient often used in making homemade ONS as a source of protein is egg white, especially in powder form (Jansen et al., 2017). Egg white consists of ovalbumin (most), ovotransferrin, ovomucoid, ovomucin, lysozyme, globulin, avidin, and cystatin. Eggs can be antibacterial, antiviral, immunomodulator, and anticancer for humans (Mine and Kovacs-nolan, 2004). Other protein sources often used are full cream milk, skim milk, or whey protein (Lestari S, Rahmawati M, Shita D, 2019). Whey protein isolate (WPI) supplementation in cancer patients receiving chemotherapy can improve nutritional status, glutathione (GSH) levels, and immunity and prevent toxicity due to chemotherapy (Bumrungpert et al. , 2018; Cereda et al., 2019; Mazzuca et al., 2019).

In addition to carbohydrates and protein, it is necessary to add food sources of fat which can be selected based on the type of fat. The type of fat that can function as an immunonutrient is an omega-3 polyunsaturated fatty acid (PUFA). High omega-3 food intake can reduce cytokines and nuclear factor- κ B (NF- κ B) through several mechanisms. One produces thromboxane A2, prostaglandins E2 and I3, and leukotriene B5, which provide anti-inflammatory effects. It can reduce the risk of complications in cancer patients (Freitas and Campos, 2019).

Another type of fatty acid is monounsaturated fatty acids (MUFA), which are more stable than PUFA and have health benefits (Vieira et al., 2015). Monounsaturated fatty acids are abundant in safflower oil and olive oil. Olive oil, besides containing MUFA, also contains high polyphenols, namely 150-400 mg/kg in m form virgin olive oil (Menendez and Lupu, 2006). In general, polyphenols have antioxidant, anti-inflammatory, antiallergic, antiatherogenic, antithrombotic and antimutagenic effects. Due to their ability to modulate cell death, olive oil polyphenols are also helpful as chemopreventive and therapeutic agents in cancer (Cárdeno et al., 2013; Gorzynik-Debicka et al., 2018).

Based on the results of preliminary research on the ONS formulation made from purple sweet potato, added whey protein, egg white powder, omega-3 powder, and olive oil, the ONS formula was obtained with an energy content of 440 kcal, 15.8 g protein (14% energy), 11.8 g fat (24% energy), carbohydrates 68.1 g (62% energy), dietary fibre 3.7 g, omega-3 164.6 mg and anthocyanins 32.8 mg per 100 g ONS powder. Combining these ingredients is expected to help increase food intake to positively affect the nutritional status and inflammatory response of HNC patients receiving radiotherapy.

B. Problem

Based on the above background, it appears that it is necessary to conduct a clinical trial of the effectiveness of purple yam-based ONS in head and neck cancer patients with radiotherapy, with research questions that can be formulated as follows:

"Is there any effect of local food-based oral nutritional supplements (ONS) containing immunonutrients (omega-3 and anthocyanins) on the nutritional status and inflammatory response of head and neck cancer patients receiving radiotherapy?"

C. Research Objectives

The general objectives and specific objectives of this study are described in the following points:

1. General purpose

The general objective of this study was to identify and analyze or study the effect of local food-based oral nutritional supplements (ONS) containing immunonutrients (omega-3 and anthocyanins) on the nutritional status and inflammatory response of head and neck cancer patients receiving radiotherapy.

2. Specific goals

This research has several specific objectives, which are described as follows:

- a. Assessing the effect of the ONS administration on nutritional status, which includes: energy and macronutrient intake, body weight, body mass index (BMI), mid-upper arm circumference (MUAC), muscle mass.
- b. Assessing the effect of giving ONS on physical function, namely grip strength.
- c. Assess the effect of the ONS administration on the patient's inflammatory response, which includes: CRP, neutrophils, lymphocytes, neutrophil/lymphocyte ratio (NLR) and IL-6.

RESEARCH METHODS

A. Research Design

This research is an experimental study using a Double-Blinded Randomized Controlled Trial design, with the intervention group receiving ONS containing immunonutrients with a composition consisting of purple yam flour, white egg flour, whey protein, olive oil, omega-3 powder, sugar, and creamer. In contrast, the control group received a standard ONS (iso-calorie) placebo with a composition of powdered skim milk, coconut oil, sugar, maltodextrin, and creamer. Each group received two packs of ONS/day @ 57 grams, brewed into 200 ml of formula with an energy content of ± 500 kcal for three weeks.

B. Population/Subject/Sample

The population in this study were MPA patients at RSUP [name], while the research subjects were these patients who met the following inclusion and exclusion criteria.

1. Inclusion criteria
 - a. Subjects diagnosed with advanced stage MPA (stages 3 and 4) who received radiotherapy or chemoradiotherapy, both as concurrent and adjuvant therapy.
 - b. Subjects aged 18-80 years.
 - c. Can consume food through a nasogastric tube (NGT) or orally.
 - d. Willing to participate in the research by signing informed consent. However, if the patient's general condition is terrible, the family is willing to sign an informed consent and help with the research.
2. Exclusion criteria
 - a. The subject has a milk or egg allergy
 - b. Subjects with comorbid renal impairment
 - c. Subjects with poor nutritional status with $BMI < 17.0 \text{ kg/m}^2$
 - d. Subject could not stand for weighing
3. Dropout criteria:
 - a. Subject died
 - b. Subjects withdrew from the study
 - c. Average ONS consumption $< 75\%$

The size of the study subjects was determined based on parameters of protein intake because one of the significant differences in the intervention and control formulas was the protein

content (Arnold and Richter, 1989; Dahlan, 2013). The minimum number of subjects in this study was 22 subjects, with an additional 20% of 5 subjects, so the number of research subjects in each group was 27 or 54 subjects.

C. Location and Time of Research

The location of this research will be carried out at dr. Sardjito Yogyakarta, with research time, will be carried out for 14 months, starting from March 2022 to April 2023.

D. Research Parameters

This study has several research parameters, which include nutritional status in the form of changes in body weight, BMI, MUAC, body composition (muscle mass), and albumin; handgrip strength as physical function; and inflammatory response in the form of CRP, complete blood profile (leukocytes, neutrophils, lymphocytes, neutrophil/lymphocyte ratio).

E. Materials and Procedures

1. Research Materials

Materials for the manufacture of ONS immunonutrients

- 1) Purple sweet potato flour made from purple sweet potato flour of the Antin 3 variety
- 2) Ovobel white egg flour
- 3) Whey protein isolate 90
- 4) Bertolli brand virgin olive oil
- 5) Omega-3 powder from Novotech Nutrition USA
- 6) Powdered sugar obtained from refined sand from the Gulaku brand
- 7) Fiber Creme brand creamer

Materials for making standard ONS:

- 1) Low-fat milk brand Tropicana Slim
- 2) Barco brand coconut oil
- 3) Powdered sugar obtained from refined sand from the Gulaku brand
- 4) Fiber Crème brand creamer
- 5) Maltodextrin

2. Research Procedures

a. Preparation of Intervention Substances (ONS Immunonutrient formula and standard ONS)

Making ONS formulas containing either immunonutrients or standard ONS is done by mixing all the ingredients using a mixer with the amount of each ingredient according to the predetermined amount. The main ingredient in this formula is purple sweet potato flour, made by drying fresh purple sweet potatoes which have been blanched beforehand.

b. Clinical Trials

A clinical trial study with a double blind, randomized controlled trial design, where there was blinding on two parties, both researchers and subjects. Disguising is done on 2 types of products by assigning a specific code to each product (eg VGYJ code for standard ONS products and KMJP code for intervention ONS products), where the coding is carried out after product packaging and labeled on aluminum foil by external parties (in outside the research team) who finalized the research product. Next, make an envelope containing each of the one codes, several research subjects to be recruited, then later 1 subject will take one envelope so that it is known that the subject belongs to a group with a specific codification. The codification is only known by external parties, which will then be stored and duplicated through hard file or soft file documents to be given to the researcher after the data has been collected and statistically analyzed. Thus, the 2 types of research products (standard ONS and intervention ONS) were unknown to either the researchers or the research subjects.

c. Storage, analysis, and reporting of research data

After collecting data, the next stage is storing, analyzing and reporting research data with the following details:

- 1) The researcher collects research data and stores it in a secure place, namely a locked cupboard and in a safe place, in terms of temperature, humidity, and attack by animals such as rats. In addition, periodically (once a week) researchers will enter research data in soft files and send them to email so that there is duplication of data or documents to avoid unwanted events. Both hard and soft file data storage is carried out in a closed and locked or password manner so that subject confidentiality is maintained and safe from the reach of other parties who have no interest in research. This is done until all the data has been collected from a large number of predetermined samples.
- 2) Researchers conducted research data analysis
- 3) Researchers report research data in the form of a dissertation

d. Possible risks that the subject will experience

For the measurement of research parameters in the form of nutritional status, it relatively does not pose a medical risk or trauma to the subject; while taking blood samples there is a risk in the form of phlebitis but this can be prevented by handling blood sampling, by a competent laboratory assistant. The product consumed by the subject was in the form of ONS or liquid food (such as milk) dense in nutrition (high in energy, high in protein, containing immunonutrients in the form of anthocyanin and omega 3), which was recommended by ESPEN as nutritional support for cancer patients undergoing radiotherapy. In addition, the consumption of products provided in the form of standard ONS or those containing immunonutrients carries a risk of digestive tract disorders, such as diarrhea, bloating, or constipation. If this happens, the subject will be referred to the doctor in charge of the study (DPJP or a radiation oncologist/dr. Sp. Onk. Rad) for examination and medication, the handling costs are the full responsibility of the researcher

F. Design of Data Processing/Analysis

The research data results were analyzed descriptively in the form of average \pm standard deviation if the data were normally distributed or median if the data were not normally distributed. The pre and post-test dependent variable data in each treatment and control group will be analyzed using a paired t-test if the data is normally distributed. Still, if the data is not normally distributed, it will be analyzed using Wilcoxon. As for the analysis of the difference between the pre and post test data then comparison between the control and intervention groups was carried out with the Independent t-test if the data was normally distributed, but if it was not normal, then it was analyzed using Mann Whitney.

G. Research Ethics

This research has received permission for ethical research feasibility from the Health Research Ethics Commission, Faculty of Medicine, Public Health and Nursing, Universitas Gadjah Mada Yogyakarta Indonesia with the number KE/FK/0996/EC/2021. Then before participating in the research, there will first be an explanation of the research's aims and objectives, the course of the research, and the benefits and risks that prospective research subjects may face. If the subject understands and agrees to participate in the study, the subject is asked to sign the informed consent that has been provided.

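### Entry and the three-week product period are not anchored to the radiotherapy course, so change scores from different radiotherapy phases can be pooled without adjustment

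*Combined protocol and SAP*

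**What the plan says.** - **Entry (Research Methods, B, inclusion criterion 1a).** Patients with stage 3 or 4 disease "who received radiotherapy or chemoradiotherapy, both as concurrent and adjuvant therapy". No start date, number of fractions delivered, fractions remaining or time since radiotherapy is given. None of the exclusion criteria refers to radiotherapy timing.
- **Product period (A. Research Design).** Two packs a day, "with an energy content of ± 500 kcal for three weeks". Neither this section nor any other says where the pre-test, the start of the product or the post-test falls in the radiotherapy course.
- **Target population (Introduction, C. Research Objectives).** The aim concerns the nutritional status and "inflammatory response of head and neck cancer patients receiving radiotherapy". This points to patients on treatment but is not an entry rule.
- **Premise (Introduction, A. Background).** "Radiation to the head and neck area causes damage to the mucosa cells and salivary glands". The next sentence reads: "It changes in taste, xerostomia, mucositis, pain, and hypophagia resulting in malnutrition". Reduced intake, weight, upper arm circumference and albumin are then named as signs of this malnutrition. All four are also outcomes of the trial (specific objectives and D. Research Parameters).
- **Allocation (E.2.b Clinical Trials).** A set of coded envelopes is prepared, "then later 1 subject will take one envelope". No stratification is described.
- **Analysis (Section F).** Paired t-test or Wilcoxon within each arm; then "the analysis of the difference between the pre and post test data then comparison between the control and intervention groups" by independent t-test or Mann-Whitney. There is no covariate.

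**The concern.** If radiation drives the loss of intake and weight, as the background says, the change over any three weeks may depend on which part of the course those weeks cover. As written, one patient could have the pre-test before or at the first fraction and another near the end of the course. Their change scores would enter the same t-test with equal standing.

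Three things are at stake:

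1. **Precision.** Differences in mean change between phases add to the variance of the between-arm comparison in a trial of 27 per arm. The added 20% in the sample size comes with no stated allowance for this.
2. **Within-arm tests.** Randomisation does not protect a pre/post comparison inside one arm. Its result depends on which phases happened to be enrolled.
3. **Target population.** The objective is about patients receiving radiotherapy, but no entry rule secures that.

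**Working it through.** **The plan's own figure.** 20% of 22 is 4.4, rounded up to 5; 22 + 5 = 27 per group, 54 in total. This matches. The base figure of 22 cannot be reproduced, because effect size, SD, alpha and power are not stated.

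**Precision, illustrated on weight change.** The documents give no SDs or phase-specific changes, so these inputs are assumptions: within-phase SD 1.5 kg; difference Δ in mean three-week change between two phases of 1.0 to 2.5 kg; share p of patients in the other phase of 20% to 50%. From the protocol: n = 27 per arm.

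Variance of the pooled change score = 1.5² + Δ²·p(1−p). SE of the arm difference = SD × √(2/27).

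| Case | Variance (kg²) | SE (kg) | Efficiency | 27 per arm acts like |
|---|---|---|---|---|
| No mixing | 2.25 | 0.408 | 1 | 27 |
| Δ = 1.0, p = 0.2 | 2.25 + 0.16 = 2.41 | 0.423 | 2.25/2.41 = 0.934 | 25.2 |
| Δ = 2.5, p = 0.5 | 2.25 + 1.5625 = 3.8125 | 0.531 | 2.25/3.8125 = 0.590 | 15.9 |

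**Chance imbalance is already in that SE.** At p = 0.5, the SD of the difference in phase share between arms is √(0.25 × 2/27) = 0.136. Times 2.5 kg, this is 0.340 kg. Then 0.408² + 0.340² = 0.531², which is the inflated SE in the last row.

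**Bias and type I error.** In a null simulation (20,000 runs, 22 per arm, three equally common phases whose mean changes differ by −1, 0 and +1 within-phase SD), the mean arm difference was −0.001 SD and the t-test rejected in 5.2% of runs at the 5% level.

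**Power, on a unit-free scale.** If 22 per arm was meant to give 80% power at two-sided 5% (an assumption), the implied standardised difference is √(2/22) × (1.960 + 0.842) = 0.845. With three equally common phases at −k, 0 and +k within-phase SDs, the SD is multiplied by √(1 + 2k²/3).

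| k | SD factor | Power at 22 per arm | n per arm for 80% |
|---|---|---|---|
| 0.25 | 1.02 | 78% | 23 |
| 0.5 | 1.08 | 74% | 26 |
| 1.0 | 1.29 | 58% | 37 |
| 1.5 | 1.58 | 43% | 55 |

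If phase is fully captured and adjusted for, power returns to about 80% at 22 per arm.

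**Within-arm tests.** With no product effect, the expected change in an arm is a weighted mean of the phase means. Moving p from 20% to 50% shifts it by 0.3 × Δ, which is 0.3 kg at Δ = 1.0 and 0.75 kg at Δ = 2.5. Enrolment mix alone can therefore move the result of a paired test.

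**The case against.** **Broad entry is a legitimate choice in a randomised trial.** This stands. The between-arm comparison is unbiased, and its type I error is nominal.

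**A reader might infer that patients who have finished radiotherapy are enrolled.** The documents do not establish this. The inference rests on the past tense *received*, but the protocol uses the past tense for planned actions elsewhere, and the objective and the risk section speak of patients receiving or undergoing radiotherapy. *Adjuvant* may describe radiotherapy given after other treatment. Completed courses are not excluded, but the point does not need them: early and late on-treatment patients can be mixed just the same.

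**A reader might infer that the three weeks run from entry.** The start is simply not stated.

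**A reader might treat chance imbalance in phase as a second harm, or as a source of false positives.** It is neither. It is the same quantity as the inflated SE, and the t-test already reflects it.

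**The premise is thin on timing.** This also stands in part. The background gives no onset, time course or recovery, and it also names the cancer itself as a cause of malnutrition. It supports a dependence on phase for intake, weight, arm circumference and albumin. It says nothing on phase for CRP, NLR, IL-6 or grip strength.

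**The size is assumed, and the low end is trivial.** Correct: 0.41 to 0.42 kg would hardly matter. The upper end needs half the patients in the other phase and a large gap. The illustration also uses weight, while the trial was sized on protein intake.

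**Narrowing entry could cost recruitment.** Also correct, with one hospital and 14 months for 54 subjects. It is a reason to prefer adjustment over a strict entry window.

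**Conclusion.** The point holds as a loss of precision and of interpretability; it is not a bias between the arms. Neither entry nor the three-week period is tied to the radiotherapy course, and neither allocation nor analysis takes phase into account. How much this costs cannot be derived from the documents. Under the assumed weight values, the SE of the arm difference rises by between 4% (0.423/0.408) and 30% (0.531/0.408). The direction rests on the protocol's own account of what radiation does. The size rests entirely on the assumed SD, phase gap and phase mix.

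The within-arm paired tests are the weaker part of Section F, because their result depends on the phases enrolled. The trial is not invalid as planned, but an adjusted analysis is better and cheap, so the change should be made.

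**What to change.** 1. **Record phase.** From the existing radiotherapy record, copy the phase at pre-test (not started; fractions delivered out of those planned; or completed, with date) and the fractions delivered by the post-test. The post-test count describes the window only. It arises after randomisation and should not enter the model.
2. **Adjust the between-arm comparison.** In Section F, replace the unadjusted test with a linear model (ANCOVA) of the post-test value on arm, pre-test value and radiotherapy phase at pre-test. Specify phase beforehand, as a category or a fraction-based term. A category is safer if any completed courses are enrolled, because a fraction count cannot tell recent from distant completion. Where an outcome is non-normal, transform or rank it and keep the same model, since the Mann-Whitney test takes no covariate.
3. **Base conclusions on that comparison.** Keep the within-arm paired tests as description at most.
4. **Match entry to the objective.** State in criterion 1a that the pre-test is taken in patients receiving radiotherapy. A narrower entry window is optional, because it may slow recruitment.

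The cost is a few extra data fields and one or two degrees of freedom for phase. Adjustment removes only the variance that the recorded phase explains. Items 1 to 3 have no recruitment cost.

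### Prespecifying adjustment for baseline value and treatment modality would sharpen the between-arm comparison; the planned unadjusted test is valid but leaves that variance in the error term

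*Combined protocol and SAP*

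**What the plan says.** Research Methods, Section B, inclusion criterion a, takes stage 3 and 4 patients "who received radiotherapy or chemoradiotherapy, both as concurrent and adjuvant therapy", with no quota for either treatment. Criterion c sets the feeding route: "Can consume food through a nasogastric tube (NGT) or orally".

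Section E.2.b describes allocation from one pool of coded envelopes: "then later 1 subject will take one envelope so that it is known that the subject belongs to a group with a specific codification". It mentions no strata, blocks or minimisation.

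Section F bases the between-group comparison on the "analysis of the difference between the pre and post test data", tested with the "Independent t-test if the data was normally distributed, but if it was not normal, then it was analyzed using Mann Whitney". It names no covariate, stratified analysis or sensitivity analysis.

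On size, Section B states: "The minimum number of subjects in this study was 22 subjects, with an additional 20% of 5 subjects", giving 27 per group and 54 in total.

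**The concern.** Modality is recorded at entry and could plausibly affect the three-week course of several outcomes: neutrophils, lymphocytes, their ratio, body weight and intake. The Background itself attributes malnutrition partly to the side effects of cancer treatment, and mentions chemotherapy toxicity alongside nutritional status and immunity. Analysing change removes baseline differences in level. It does not remove a different trajectory under chemotherapy, and it does not use whatever the baseline value predicts about the change.

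At stake is precision in a trial expecting about 22 evaluable subjects per arm, and how the single realised estimate is read if the arms happen to differ in modality.

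**Working it through.** **The plan's own figure.** 20% of 22 is 4.4, rounded up to 5; 22 + 5 = 27 per arm, and 2 × 27 = 54. This reproduces. The 22 cannot be reproduced, because no effect size, SD, alpha or power is stated.

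**Assumed inputs.** The documents give neither the share *p* on chemoradiotherapy nor its effect *g* on change. I take *p* = 0.5-0.7 and *g* = 0.5-1.0 within-modality SD.

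**Chance of an imbalance of 20 points or more, 27 per arm.**
- Two independent Binomial(27, *p*) counts: 13.4%, 12.6% and 10.1% for *p* = 0.5, 0.6, 0.7.
- If the envelopes are a fixed set of 27 per code, P(x) = C(K,x)·C(54−K,27−x)/C(54,27), with gap |2x−K|/27. For K = 27, 32, 38 this gives 10.2%, 16.6% and 13.5%. The values are uneven because only certain gaps can occur.
- At 22 per arm the independent-draw figures are 14-17%.

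**Shift from a 20-point gap, in total-SD units:** 0.20·g/√(1 + p(1−p)g²). At *p* = 0.6:
- *g* = 0.5: 0.10/√1.06 = 0.10
- *g* = 0.8: 0.16/√1.154 = 0.15
- *g* = 1.0: 0.20/√1.24 = 0.18

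For scale, the standard error of the arm difference at 22 per arm is √(2/22) = 0.30 SD, so a 0.15 SD shift is about half a standard error.

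**Gross variance share of modality:** p(1−p)g²/(1 + p(1−p)g²) = 5-6% at *g* = 0.5, 12-14% at 0.8 and 17-20% at 1.0. The net gain is smaller, because covariates use degrees of freedom and are themselves imperfectly balanced.

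**Type I error** (20,000 simulated trials, 22 per arm, *p* = 0.5). Over all draws the unadjusted t-test rejects 5.0% (*g* = 0.5) and 5.2% (*g* = 1.0) of the time. Restricted to draws with a gap of 27 points or more, it rejects 6.9% and 12.4%. With modality as a covariate those become 5.5% and 5.1%.

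**Power** (22 per arm, *p* = 0.6, assumed product effect 0.87 SD, two-sided 5%). Two separate simulations; the second used 10,000 trials per setting (Monte Carlo error about 0.4 point).

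| Modality effect | Unadjusted (run 1 / run 2) | Modality only (run 1 / run 2) |
|---|---|---|
| 0 | 81% / 80% | 80% / 79% |
| 0.5 SD | 78% / 78% | 79% / 79% |
| 0.8 SD | 74% / 74% | 80% / 79% |
| 1.0 SD | 72% / 71% | 79% / 79% |

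Modality alone therefore gains 5-6 points at 0.8 SD and 7-8 at 1.0 SD.

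With baseline value and modality together (run 2), power is about 78% if baseline says nothing about change, 82-83% if the two correlate 0.3 in size, and 88-89% if they correlate 0.5. Adding feeding route as well (run 1) gives 77-78%, about 81% and 87-88%.

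**The case against.** The strongest reply is that randomisation already deals with this. A two-sample test on change is valid after simple randomisation, and its standard error already allows for chance imbalance. That stands: type I error is about 5% over all draws. A reader might infer from the mixed population and single draw that the comparison is biased or the test invalid. The documents do not support that. The 12.4% figure holds only for draws with a large gap and an assumed 1.0 SD modality effect.

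A second reply is that the benefit depends on unknown inputs and can vanish. This also stands. At a 0.5 SD modality effect with an uninformative baseline, the two-covariate model gives about 78% power, the same as no adjustment. If neither covariate matters, it loses 1-2 points. The gross 12-14% variance share should not be read as an equal gain in sample size.

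Third, feeding route. It might seem to deserve the same treatment as modality, but the documents give no share of tube-fed patients and no basis for an effect, and the covariate may be sparse.

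These replies do not remove the asymmetry: the possible loss is small and bounded, while the gain is material if either covariate is moderately prognostic. Adjusting only after an imbalance is seen would leave the choice of covariates open to selection; naming them beforehand avoids that.

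**Conclusion.** This is an optional improvement in precision, not a defect that invalidates the analysis. The plan mixes two treatment modalities, mentions no strata and names no covariate. The point about strata rests on the plan's silence.

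The probability of a gap of 20 points or more depends on the assumed modality share and on how the envelopes are made up: 10-13% with independent draws, up to 17% with a fixed set. The shift of 0.10-0.18 SD and the power gain of about 5-8 points rest on assumed modality effects, of 0.5-1.0 SD and 0.8-1.0 SD respectively. Any further gain depends on how well baseline predicts change.

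It would go too far to infer that the allocation must be stratified: adjustment in the analysis recovers most of the benefit. The validity statement concerns the arms as randomised. Removing subjects with average consumption below 75% is a separate matter that these covariates do not resolve.

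**What to change.** Keep the single envelope draw. In Section F, make the between-arm analysis of each outcome a prespecified ANCOVA with two covariates: the baseline value, and modality at entry (radiotherapy alone versus chemoradiotherapy). With baseline in the model, using the post value or the change as response gives the same arm difference. Where Mann-Whitney was planned, use a log-transformed or rank-based ANCOVA, and state in advance which outcomes that covers.

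Tabulate modality and baseline feeding route by arm. Add feeding route as a covariate only in a sensitivity analysis.

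Cost: a short paragraph in Section F and a recorded modality and feeding route for each subject, both of which bear on the eligibility check. At 22 per arm the residual degrees of freedom fall from 44 − 2 = 42 to 40, with a power loss of about 1-2 points if neither covariate is prognostic. Allocation and clinical management do not change.

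### Inclusion criterion 1d ties a family signature to an undefined physical state rather than to loss of capacity, while Section G describes only the subject signing; the two passages need one consent rule

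*Combined protocol and SAP*

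**What the plan says.** Inclusion criterion 1d (Section B, Population/Subject/Sample) opens with the usual default, that the patient is "Willing to participate in the research by signing informed consent". Its next sentence makes an exception: "if the patient's general condition is terrible, the family is willing to sign an informed consent and help with the research".

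Section G (Research Ethics) sets out the consent procedure. The study is explained first, including "the benefits and risks that prospective research subjects may face". Then: "If the subject understands and agrees to participate in the study, the subject is asked to sign the informed consent that has been provided". No other signatory appears there.

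Two other entries in Section B describe who can be in the trial. The age criterion is "Subjects aged 18-80 years", and exclusion 2d removes a patient for whom "Subject could not stand for weighing" applies.

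**The concern.** A family signature in place of the patient's own is normally justified by the patient's inability to understand or decide. Criterion 1d uses a different test, how unwell the patient is. Many patients with advanced head and neck cancer under radiotherapy may be physically very unwell and still able to make their own decision. An investigator with such a patient would find a family route in the eligibility criteria and none in the ethics section.

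What is at stake is whether someone able to agree or refuse is asked to do so before joining a trial. Participation involves blood sampling, for which the protocol states a risk of phlebitis. It also involves two packs a day for three weeks of a study product with stated risks of diarrhoea, bloating or constipation.

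**Working it through.** No arithmetic applies: the point depends on no rate, effect size, power or sample size, and the plan gives no figure to reproduce. The check is a comparison of the two passages and a search of the rest of the document for anything that reconciles them.

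| Question | Criterion 1d | Section G |
|---|---|---|
| Who signs? | The patient by default; the family in the exception | The subject |
| Whose willingness is named? | The patient's by default; the family's in the exception | The subject's |
| What triggers a family signature? | A very poor general condition | No family route is given |
| How is the trigger defined, and who judges it? | Not stated | Not applicable |
| Is capacity to decide mentioned? | No | Only indirectly, since the subject must have understood |
| Is the family mentioned in connection with the explanation? | No | No |

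Step 1. The default in 1d agrees with Section G. The difference lies wholly in the exception.

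Step 2. The exception turns on general condition. It is not defined, no assessor is named, and it is not tied to understanding or decision-making.

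Step 3. Could the exception be there for people who cannot consent for another reason? Age does not explain it, because every participant is an adult of 18 to 80. Exclusion 2d does not explain it either. Anyone eligible can stand to be weighed, so a patient who meets the exception and is still eligible may well be able to decide. Exclusion 2d therefore limits how ill an entrant can be, but it does not confine the exception to patients without capacity.

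Step 4. No other visible part of the document gives a capacity assessment, a rule on assent, a witness for a patient who cannot write, a definition of an authorised representative, or consent from the patient on recovery. Nothing visible reconciles 1d with Section G.

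Result: the two passages differ on who may sign, and the wording of 1d leaves room for a relative to sign in place of a patient who has capacity.

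**The case against.** Four points on the other side have weight.

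First, Section G may simply be a general summary that leaves out an exception stated elsewhere. That would make it incomplete rather than contradictory, and its wording is that the subject is asked to sign, not that only the subject may. This is fair, and it is why the point is put as a difference to be reconciled. It does not help with the trigger, which remains unrelated to capacity.

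Second, 1d can be read as a relative signing for, and helping, a weak patient who is willing. A reader might infer the opposite, that the protocol enrols competent patients without their agreement. The documents do not support that inference: 1d nowhere says that the patient's willingness is waived, patients may withdraw, and nothing shows that anyone entered this way. Equally, 1d does not state the benign reading; in the exception it names only the family's willingness.

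Third, the consent pages are not in the public file and may hold a rule on capacity or representatives. Ethics approval is also reported. Both limit what can be concluded about practice, but neither brings the two protocol passages into line.

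Fourth, a reader might go on to infer harm to the data: that patients entering by this route would use up the allowance of 5 per group (27 planned against a minimum of 22), or that 1d contradicts exclusion 2d. Neither follows. Who signs does not change how ill the patient is, and an equally ill patient who signs in person is just as eligible and just as likely to be lost. The listed dropout criteria are death, withdrawal and average consumption below 75%; a missing grip-strength or weight reading is not among them, and the sample size rests on protein intake. The documents give no number of such entrants and no loss rate for them. Exclusion 2d and criterion 1d are cumulative filters, and a patient can be very unwell and still able to stand briefly.

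**Conclusion.** The concern holds as a consent-wording problem that should be corrected. Criterion 1d permits a family signature on an undefined physical trigger, Section G describes only the subject's own agreement and signature, and no visible text joins the two. The consequence is a possibility left open by the wording: a very ill adult who can still decide could be randomised on a relative's signature alone.

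The size cannot be expressed as a number, and no effect on sample size, error rates or the planned analysis is claimed. The conclusion rests on the visible text and allows that the consent form may already contain a suitable rule.

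**What to change.** Replace the exception in 1d with a rule based on capacity, and state the same rule in Section G:

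- The subject's own consent is required whenever the subject has capacity to decide, however ill.
- A family member may witness or write for a subject who agrees but cannot physically sign.
- Family consent in place of the subject's applies only when the subject lacks capacity, with the subject's assent sought.

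The amended text should also say who judges capacity, and the consent form should be checked against it.

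The cost is a short protocol amendment with ethics notification, and possibly a few fewer very ill entrants. Endpoints, products, schedule and analysis are unchanged.
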